3.6.1 Adverse events

Adverse events experienced by the subjects will be collected throughout the entire study, including the second year extension period, and will be coded using the latest version of MedDRA.

Adverse event data will be categorised according to their onset date into the following study periods:

- AEs occurring during screening:
An AE during screening is defined as an AE with a date of onset \geq date of the screening visit and date and time of onset $<$ date and time of the first dose of IP.
AEs occurring during screening will only be listed.
- AEs occurring during treatment:
An AE during treatment is defined as an AE with a date and time of onset \geq date and time of first dose of IP and \leq date of last dose of IP + 28 days.
- AEs occurring during follow-up:
An AE during follow-up is defined as an AE with a date of onset $>$ date of last dose of IP + 28 days and \leq date of last dose of IP + 84 days.
- AEs occurring after follow-up:
An AE after follow-up is defined as an AE with a date of onset $>$ date of last dose of IP + 84 days.
AEs occurring after follow-up will only be listed.

If an AE has a missing onset date, then unless the stop date of the AE indicates otherwise, this will be considered as an AE during treatment. Similarly, if an AE has a partial onset date, then unless the partial onset date or the stop date indicates otherwise, this will be considered an AE during treatment.

Adverse events with missing intensity will be assumed to be severe. Events with missing relationship to study medication per the investigator will be assumed to be related. If no information about seriousness is available, the AE will be considered serious.

An acute AE is defined as an AE with a date of onset on any day of administration of IP and a time of onset on or after the start of administration of IP or a date of onset occurring on the subsequent day. If an AE has a missing onset date, then unless the stop date of the AE indicates otherwise, this will be considered as an acute AE. Similarly, if an AE has a partial onset date, then unless the partial onset date or the stop date indicates otherwise, this will be considered acute AE.

Adverse events during treatment will also be presented by time intervals of the first onset of the event. For this analysis, repeated events with the same preferred term will not be considered (i.e. if a subject has more than one event with the same preferred term, only the event with the earliest date of onset will be used). For partial or missing dates, the rules as described above will be used. The following time intervals (defined as exact weeks, independent of the study visits and with no visit windowing) are defined:

- Day 1 to $<$ Week 12:
AEs with date of onset \geq date of first administration of IP and $<$ date of first administration of IP plus 84 days

- Week 12 to < Week 24:
AEs with date of onset \geq date of first administration of IP plus 84 days and < date of first administration of IP plus 168 days
- Week 24 to < Week 36:
AEs with date of onset \geq date of first administration of IP plus 168 days and < date of first administration of IP plus 252 days
- Week 36 to < Week 48:
AEs with date of onset \geq date of first administration of IP plus 252 days and < date of first administration of IP plus 336 days
- Week 48 to < Week 60:
AEs with date of onset \geq date of first administration of IP plus 336 days and < date of first administration of IP plus 420 days
- Week 60 to < Week 72:
AEs with date of onset \geq date of first administration of IP plus 420 days and < date of first administration of IP plus 504 days
- Week 72 to < Week 84:
AEs with date of onset \geq date of first administration of IP plus 504 days and < date of first administration of IP plus 588 days
- Week 84 to < Week 96:
AEs with date of onset \geq date of first administration of IP plus 588 days and < date of first administration of IP plus 672 days
- Week 96 to < Week 100:
AEs with date of onset \geq date of first administration of IP plus 672 days and < date of first administration of IP plus 756 days
- \geq Week 100:
AEs with date of onset \geq date of first administration of IP plus 756 days

The event rate per 100 subject years is defined as the number of subjects with an event divided by the sum of exposure time in days (e.g. date of last dose of IP + 28 days - day of first dose of IP + 1 day for summary of AEs during treatment) for all subjects in the analysis set multiplied by 365.25 days/year multiplied by 100.

The time to first onset of herpes zoster during treatment will be derived as date of first onset of herpes zoster – date of first administration of IP + 1. AEs with an onset date before the date of first administration of IP and AEs with an onset after 28 days after the date of last administration of IP will not be considered for the time to first onset of herpes zoster during treatment. If a subject has no herpes zoster during treatment, the time to first onset will be censored at the date of last administration of IP + 28 days.

For herpes zoster, an alternative event rate per 100 subject years will be derived as the number of subjects with herpes zoster divided by the sum of time at risk in days for all subjects in the analysis set multiplied by 365.25 days/year multiplied by 100. The time at risk is defined as time (including start and end date) from start of period (e.g. date of first administration of IP for events during treatment) to the date of first event, discontinuation or completion of the

study, or the database extract date, whatever comes first. This alternative event rate may also be calculated for other AESIs if suggested by data. This will be discussed during the BDR meeting and the decision will be made before unblinding the data.

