3.9.9 Procedures for discontinuation of a subject from investigational product

Discontinuation of IP does not necessarily mean discontinuation of follow-up or termination of study participation. Subjects who are discontinued from the IP should be followed up to continue to undergo all study-related visits/procedures for the full treatment period (Table 2) in order to support the final efficacy and safety analysis for anifrolumab (see Section 8). Subjects who discontinue IP earlier than 12 weeks before Week 52 will be followed until Week 52. Those discontinued within 12 weeks prior to Week 52 will need to have follow-up beyond Week 52 to complete a 12 week safety observation period after the last dose of IP administration.

Subjects who discontinue IP in the second year extension period will be followed until Week 104. Those discontinued within 12 weeks prior to Week 104 will need to have follow-up beyond Week 104 to complete a 12-week safety observation period after the last dose of IP administration.

The reason for premature discontinuation of IP will be documented in the source documents and recorded in the eCRF.

It is essential to collect as much data as possible for all subjects throughout the study and especially all potential endpoint events. Complete withdrawal from the study (ie, withdrawal of consent) has a direct negative impact on the potential validity of all study data and should be avoided wherever possible. If the subject permanently discontinues IP prior to their completion of the study and wishes to continue with only selected study assessments; prioritised assessments are listed in Section 4.2.2.

For subjects who wish to withdraw from the study completely refer to Section 3.9.4.

If a subject is withdrawn from study, see Section 3.10.

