4.2.6.1 Adverse Events

If not stated otherwise, all summaries described below will be presented separately for

- AEs during treatment
- AEs during follow-up

For summaries during follow-up, only subjects with any study documentation after the date of last dose of IP + 28 days will be considered.

An overall summary of subjects with at least one AE in the following categories will be presented, and will include the event rate per 100 subject years, and total exposure in years for each treatment group:

- Any AE
- Any acute AEs
This category will not be included in the summary during follow-up.
- Any AE with outcome = death
- Any SAE (including events with outcome = death)
- Any AE leading to discontinuation of IP
 - This category will not be included in the summary during follow-up.
- Any AE related to IP by investigator's judgement
- Any AE of severe intensity
- Any AESI
 - Any AESI of non-opportunistic serious infections
 - Any AESI of opportunistic infections
 - Any AESI of anaphylaxis
 - Any AESI of malignancy
 - Any AESI of herpes zoster
 - Any AESI of tuberculosis
 - Any AESI of influenza
 - Any AESI of vasculitis (non-SLE)
 - Any AESI of major acute cardiovascular events (MACE as adjudicated)
- Any other significant AE

The number and percentage of subjects with at least one AE (i.e. multiple occurrences of an AE in 1 subject will only be counted once) will be summarised by MedDRA system organ class and preferred term (unless specified otherwise) for the following AE categories. These summaries will also include the event rate per 100 subject years and total exposure in years for each treatment group (unless specified otherwise).

- Any AE
- Any AE above reporting threshold of 2% of subjects in any treatment group in the full analysis set.
This summary will be presented by preferred term for AEs during treatment only.
- Any non-serious AE above reporting threshold of 5% of subjects in any treatment group in the full analysis set
This summary will not include the event rate per 100 subject years and total exposure in years.
- Any SAE with outcome = death
This summary will be presented for SAEs with an outcome of death during the treatment and follow-up periods combined.
- Any SAE (including events with outcome = death)
- Any AE leading to discontinuation of IP
This summary will be presented for AEs during treatment only.
- Any AE by relationship to IP (yes, no)

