(multiple occurrences of an AE in 1 subject will only be counted once as related if at least one AE is related and as not related if all occurrences are not related)
This summary will be presented for AEs during treatment only.
- Any AE by maximum intensity (mild, moderate, severe)
(i.e. multiple occurrences of an AE in 1 subject will only be counted once with the maximum intensity in this AE)
This summary will be presented for AEs during treatment only.
- Any AESI
This summary will not be presented by system organ class but by AESI category (non-opportunistic serious infections, opportunistic infections, anaphylaxis, malignancy, herpes zoster, tuberculosis, influenza and vasculitis [non- SLE]).
- Any other significant AE
This summary will be presented for AEs during treatment only.
- Any AE by time interval (as detailed in Section 3.6.1) for the first onset of event
This summary will be presented for AEs during treatment only.

Cardiovascular outcome events as determined by the Cardiovascular Event Adjudication Committee will be presented separately, summarising the number of AEs submitted for adjudication and the outcomes of the adjudication including MACE classification. Site reported cardiovascular AEs, cardiovascular SAEs and their corresponding adjudicated outcomes will be listed.

The time to first onset of herpes zoster during treatment will be presented as a Kaplan-Meier plot including the number of subjects at risk at each visit.

Furthermore, the alternative event rates per 100 subject years for herpes zoster (and possible other AESIs) will be summarised for events during screening, during treatment, and during follow-up. The total time at risk will also be presented.

An overall summary of subjects with AE's in pre-specified categories will also be presented by ADA category.

Key subject information for subjects with an AE with outcome of death, subjects with serious AEs, subjects with an AE leading to discontinuation of IP, subjects with cardiovascular events and subjects with AESIs, respectively, will be provided.

All AEs and AEs in ADA positive (at any time) subjects will be listed.

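### For subjects who stop IP early, AEs starting more than 84 days after the last dose are collected but left out of the by-arm AE, SAE, AESI and death tables

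*SAP*

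**What the plan says.** SAP 3.6.1 sorts AEs by onset date. The treatment period ends at "date of last dose of IP + 28 days" and the follow-up period at "date of last dose of IP + 84 days". For any later onset the rule is "AEs occurring after follow-up will only be listed".

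SAP 4.2.6.1 opens its tables with a default, "If not stated otherwise, all summaries described below will be presented separately for", followed by two periods only: during treatment and during follow-up. The SAE and AESI tables (malignancy and opportunistic infection among the categories) state no exception that brings in later events. The table of fatal SAEs departs from the default only by merging the two periods: "This summary will be presented for SAEs with an outcome of death during the treatment and follow-up periods combined". Adjudicated cardiovascular events have their own presentation, with no period stated: "Cardiovascular outcome events as determined by the Cardiovascular Event Adjudication Committee will be presented separately".

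The protocol observes early stoppers for longer than this. Section 3.9.9 keeps them on study visits "in order to support the final efficacy and safety analysis for anifrolumab". For the first year it says "Subjects who discontinue IP earlier than 12 weeks before Week 52 will be followed until Week 52", and it makes the parallel provision to Week 104 for the second year. Sections 6.5.1 and 6.7 collect AEs, SAEs and AESIs to the end of participation, and Section 4.2.2 puts AEs, including AESIs, on the minimum list of assessments after IP is stopped.

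**The concern.** The 84-day limit suits a subject who finishes dosing and then leaves the study 12 weeks later. It does not suit a subject who stops IP part-way through a year and stays to Week 52 or Week 104. For that subject, part of the safety observation the protocol asks for, sometimes most of it, feeds no by-arm AE comparison.

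The design itself creates such subjects through the stopping criteria in Protocol 3.9.1 and 3.9.2. Protocol 6.4.4 treats malignancy risk as central to the benefit-risk profile, and a malignancy need not declare itself within 12 weeks of a dose. Stopping happens after randomisation, so if its rate or reasons differ between arms, the untabulated time will differ too. The documents give no information on whether that will happen.

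**Working it through.** **Inputs.** Scheduled days from SAP Table 2: Week 0 = Day 1, Week 8 = Day 57, Week 20 = Day 141, Week 48 = Day 337, Week 52 = Day 365, Week 60 = Day 421, Week 100 = Day 701, Week 104 = Day 729, Week 112 = Day 784. The period limits of 28 and 84 days come from SAP 3.6.1. The end of observation for early stoppers comes from Protocol 3.9.9: Week 52 or Week 104, or 12 weeks after the last dose if that is later.

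**The plan's own figure.** 84 / 7 = 12 weeks, which is the planned safety follow-up. From the Week 48 dose, 337 + 84 = 421, exactly the Week 60 visit day. From the Week 100 dose, 701 + 84 = 785, one day past the Week 112 visit day of 784. The cut therefore reproduces the planned follow-up of subjects dosed on schedule, who lose essentially nothing.

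**Early stoppers.** For a last dose at Week w, the listed-only time is 52 − (w + 12) = 40 − w weeks in year 1 and 104 − (w + 12) = 92 − w weeks in year 2, never below zero.

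| Last dose | Tabulated to | Observed to | Listed only |
|---|---|---|---|
| Week 0 | Week 12 | Week 52 | 40 weeks |
| Week 8 | Week 20 | Week 52 | 32 weeks |
| Week 20 | Week 32 | Week 52 | 20 weeks |
| Week 36 | Week 48 | Week 52 | 4 weeks |
| Week 40 | Week 52 | Week 52 | 0 |
| Week 52 | Week 64 | Week 104 | 40 weeks |
| Week 60 | Week 72 | Week 104 | 32 weeks |
| Week 80 | Week 92 | Week 104 | 12 weeks |
| Week 92 | Week 104 | Week 104 | 0 |

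The gap thus exists for last doses before Week 40 in year 1, and from Week 52 to before Week 92 in year 2.

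**In days.** Weeks 8 and 20 are the last doses if IP is withheld at the Week 12 and Week 24 stopping visits.

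- Last dose Week 8: 57 + 84 = 141; 365 − 141 = 224 listed-only days out of 365 − 57 = 308 post-dose days, or 73%.
- Last dose Week 20: 141 + 84 = 225; 365 − 225 = 140 of 365 − 141 = 224, or 62.5%.
- Last dose Week 60: 421 + 84 = 505; 729 − 505 = 224 of 729 − 421 = 308, or 73%.

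**Across the trial.** The documents give no discontinuation rate. Assume, for scale only, that 10% to 30% of 150 subjects stop in year 1 with a last dose at Week 8 to Week 20.

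- Low end: 15 subjects × 20 weeks × 7 / 365.25 = 5.7 person-years.
- High end: 45 subjects × 32 weeks × 7 / 365.25 = 27.6 person-years.
- Total year-1 observation: 150 × 364 / 365.25 = 149.5 person-years.

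**Other safety outputs in the SAP.** Section 4.2.6.4 summarises off-treatment extra-renal flares with no upper day limit. Section 3.6 counts other safety values as on-treatment up to the Week 104 visit or the last visit. The 84-day limit is therefore not a general principle of the safety analysis.

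**The case against.** The strongest defence is that 84 days is the protocol's own safety window. Protocol 1.4 sets safety follow-up at 12 weeks, Section 3.9.9 uses the same 12 weeks as its safety observation period, and Section 8.5.4 asks for AE summaries by treatment and follow-up period. The SAP carries that out openly. This stands: the existing tables are sound, and the point is a missing complement to them, not a contradiction between the documents.

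A reader might infer that late deaths and cancers vanish from the report. They do not. SAP 4.2.6.1 lists all AEs and gives key information, with no date limit, for each subject with a fatal AE, an SAE, an AESI or a cardiovascular event. SAP 4.1.3 sorts listings by treatment group. Study withdrawals are tabulated by arm with reasons (SAP 4.2.5.1). The cardiovascular committee reviews deaths from any cause (Protocol 6.4.9), so a late death may be counted in the adjudicated table, although the default in SAP 4.2.6.1 could be read to restrict that table as well. With about 150 subjects, such material can be read by hand. None of it, however, is a by-arm summary of late SAEs, malignancies or infections.

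A reader might also infer that every death after day 84 drops out of the death table. The rule works on AE onset, so a late death from an AE that began by day 84 stays in. An AE with a missing onset date defaults to the treatment period unless its stop date says otherwise.

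Nor is there a general loss for completers. It takes the Week 48 dose 7 days early and the Week 60 visit 7 days late to reach (421 + 7) − (337 − 7) = 98 days, which is 14 beyond the cut.

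Finally, later events may follow rescue immunosuppression, which Protocol 3.9.1 permits after IP is stopped. A whole-study table would mix those effects with the effect of randomised IP. That limits how such a table can be read but is not a reason to omit it.

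**Conclusion.** The concern holds for early stoppers only. If their last dose falls before Week 40 in year 1, or from Week 52 to before Week 92 in year 2, AEs with onset beyond day 84 are collected but enter none of the by-arm AE, SAE, AESI or fatal-SAE tables. The adjudicated cardiovascular table is a possible exception. The loss is at most 40 weeks per subject.

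The per-subject figures follow from the scheduled days and assume that the subject remains under observation to Week 52 or Week 104. The total of roughly 6 to 28 person-years rests wholly on an assumed stopping rate. The documents do not show that the omission would differ between arms; that is a possibility, not a finding. The gap is worth closing because the data are already collected for a stated safety purpose.

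**What to change.** Keep the treatment and follow-up tables as they are. In SAP 3.6.1 and 4.2.6.1:

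- Add one by-arm summary of deaths, SAEs, malignancy and opportunistic infection, from first dose to the end of study participation, with total observation time as the denominator for rates.
- Extend the fatal-SAE table to the same period.
- State that the adjudicated cardiovascular (MACE) table covers the whole study.

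The cost is a short SAP amendment before unblinding and a few tables from data already collected. The price in interpretation is that the new tables mix time on and off IP and may include events after rescue immunosuppression. They should be labelled accordingly and read as supplementary to the on-treatment tables.

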4.2.5 Presentation of study population

4.2.5.1 Subject disposition

The number and percentage of subjects randomised, randomised but not treated with IP, and not randomised will be summarised by treatment group for the all subjects analysis set.

The number and percentage of subjects completing the double-blind treatment period of the study up to and including Week 52 and the number and percentage of subjects withdrawing from the study during the double-blind treatment period including reason for withdrawal, will be summarised by treatment group for the full analysis set .

The number and percentage of subjects completing treatment with IP during the double-blind treatment period up to and including Week 48 (i.e. with last administration of IP at Visit 13), the number and percentage of subjects permanently discontinuing the treatment with IP during the double-blind treatment period including reason for withdrawal, and the number and percentage of subjects who discontinued the treatment with IP after completing treatment with IP in the double-blind treatment period and did not enter the second year extension period including reason for withdrawal, will be summarised by treatment group for the full analysis set.

The number and percentage of subjects continuing into the second year extension period of the study from Week 52 up to and including Week 112 will be summarised by treatment group for the full analysis set.

The number and percentage of subjects completing the second year extension period of the study from Week 52 up to and including Week 112 and the number and percentage of subjects withdrawing from the study during the second year extension period including reason for withdrawal, will be summarised by treatment group for subjects who continued in the second year extension period.

The number and percentage of subjects completing treatment with IP during the second year extension period from Week 48 up to and including Week 100 (i.e. with last administration of IP at Visit 26) and the number of subjects permanently discontinuing the treatment with IP during the second year extension period including reason for withdrawal, will be summarised by treatment group for the subjects who continued into the second year extension period.

The number and percentage of subjects not continuing into the second year extension period of the study including reason for not continuing, will be summarised by treatment group for the full analysis set.

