The number and percentage of subjects completing the study up to and including Week 112 and the number and percentage of subjects withdrawing from the study including reason for withdrawal, will be summarised by treatment group for the full analysis set.

The number and percentage of subjects completing treatment with IP up to and including Week 100 (i.e. with last administration of IP at Visit 28) and the number of subjects

permanently discontinuing the treatment with IP including reason for withdrawal, will be summarised by treatment group for the full analysis set.

A summary of number and percentage of subjects in each country and each site by treatment group and overall will be provided for the full analysis set.

Summaries of important protocol deviations and analysis sets will be provided.

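### In SAP 3.6.1 the labels and day limits of the last two adverse-event onset intervals conflict (Week 100 is 700 days, not 756), and SAP 4.2.5.1 ties Week 100 completion to the Week 92 visit

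*SAP*

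**What the plan says.** SAP 3.6.1 introduces the table as follows: "Adverse events during treatment will also be presented by time intervals of the first onset of the event". The intervals are "defined as exact weeks, independent of the study visits and with no visit windowing". Only the earliest onset per preferred term per subject is counted.

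The second-to-last interval is labelled "Week 96 to < Week 100". Its limits are the date of first administration "plus 672 days and < date of first administration of IP plus 756 days". The last interval, labelled as Week 100 and later, begins at "date of first administration of IP plus 756 days".

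SAP 4.2.6.1 makes this a reported output, "Any AE by time interval (as detailed in Section 3.6.1) for the first onset of event", restricted to events during treatment. SAP 3.6.1 ends that period 28 days after the last dose.

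SAP 4.2.5.1 describes completion of second-year treatment through Week 100 as "with last administration of IP at Visit 26". Later in the same section, completion of all treatment through the same Week 100 is "with last administration of IP at Visit 28".

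**The concern.** These are programming rules for tables that will be reported. In the adverse-event table, label and day limits cannot both be followed. A programmer who follows the days prints events that began at or after Week 100 under a heading saying they began before it, and will normally print nothing in the row from Week 100 on. A reader of the table could take this as a cluster of new events just before Week 100 followed by none, when both features come from the definition. A programmer who follows the labels departs from the written rule, and two programmers could resolve the conflict differently.

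The visit number raises the same kind of problem for disposition. Read literally, a subject whose last infusion was at Week 92 counts as having completed second-year treatment, and a subject dosed through Week 100 does not match the definition.

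**Working it through.** **1. The interval boundaries.** Exact weeks from first dose give boundary = 7 × week number.

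| Week | 7 × week | SAP 3.6.1 |
|---|---|---|
| 12 | 84 | 84 |
| 24 | 168 | 168 |
| 36 | 252 | 252 |
| 48 | 336 | 336 |
| 60 | 420 | 420 |
| 72 | 504 | 504 |
| 84 | 588 | 588 |
| 96 | 672 | 672 |
| 100 | 700 | 756 |

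Eight of the nine boundaries reproduce exactly. The ninth does not: 756 / 7 = 108. Counting by study day instead does not help, since SAP Table 2 puts Week 100 at day 701 and Week 108 at day 756.

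**2. Width of the second-to-last row.** By its label: (100 − 96) × 7 = 28 days. By its limits: 756 − 672 = 84 days.

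**3. Latest possible on-treatment onset.** This is the last-dose day plus 28 (SAP 3.6.1). The last dose is at Week 100 (protocol 4.2.1.3), and there is no dosing at Week 104 (protocol Table 4, footnote g).

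- On schedule: 700 + 28 = 728.
- At the end of the 7-day visit window (protocol Table 4): 707 + 28 = 735.
- At the end of the SAP Table 2 window for Week 100 (study day 714, so 713 days after first dose): 713 + 28 = 741.
- Dose resumed 14 days late (protocol 6.11.2): 714 + 28 = 742.

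All four are below 756. For an onset to reach day 756, the last dose must fall at 756 − 28 = 728 days or later. That is Week 104, 28 days past the Week 100 target.

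**4. Where the events go.** On-treatment onsets from day 700 to day 728 (742 at the latest) fall inside 672 to under 756, so they are printed under the label ending at Week 100. On schedule, the row covers 728 − 672 = 56 days of on-treatment time rather than 28.

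**5. The visit number.** Protocol Table 4 starts at Visit 17 = Week 56 and adds one visit every four weeks.

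- Visit 26: 56 + 4 × (26 − 17) = Week 92.
- Visit 28: 56 + 4 × (28 − 17) = Week 100.

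Protocol 7.1 and 7.2.1 also end the dosing visits at Visit 28.

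**The case against.** **The label may be the slip, not the day count.** All eight preceding intervals are 84 days wide, and 672 to under 756 is also 84 days. If a 12-week interval was intended, no event is misallocated against it and only the headings are wrong. This stands: the documents do not settle the direction, so the finding is that label and rule conflict. A reader might infer that 756 was meant as Week 100; the text does not show that.

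**The last row need not always be empty.** On-treatment time follows the actual last dose, so an infusion four or more weeks late could put an event there. SAP 3.6.1 also treats events with missing or partial onset dates as on-treatment unless other dates indicate otherwise, and applies that rule to this table. This stands too: the row is empty under protocol-compliant dosing with complete onset dates, not by mathematical necessity.

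**Twice the time does not mean twice the count.** A reader might infer from 56 against 28 days that the row's counts double. Only first onsets per preferred term are kept, so late repeats drop out, and the documents give no event rate. Only the time span is established.

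**Nothing is lost.** The same events appear in the overall, system organ class, serious, intensity and special-interest summaries and in the listings; later onsets go to the follow-up summaries. Correct, and it limits the importance of the point.

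**The Visit 26 sentence names Week 100 itself.** A careful programmer would probably use Visit 28. That makes a wrong count possible rather than certain, but the sentence still contradicts itself and the overall summary in the same section.

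**Conclusion.** The point holds as an inconsistency to reconcile. As written, a row labelled as 28 days spans 84 and absorbs on-treatment onsets at Week 100 or later. The row from Week 100 on is empty given protocol-compliant dosing and complete onset dates, because on-treatment time ends at about day 728 and at most about day 742. In the second-year disposition summary, the visit cited for Week 100 is the Week 92 visit.

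The effect is limited to one descriptive adverse-event table, in which only subjects treated in the second year can normally contribute to these rows, and to the second-year completion count. A reader might infer that safety events go unreported or that the main results are at risk. The documents support neither: overall adverse-event summaries, the overall completion count, the primary analysis, alpha and power do not use these definitions.

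**What to change.** In SAP 3.6.1, replace 756 with 700 in both bullets and keep the labels. The rows then cover 672 to under 700 days and 700 days onward, and the last row holds on-treatment onsets from day 700 to about day 728 (742 at the latest).

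Alternatively, use a single final interval from Week 96 (672 days onward). This stays close to the 12-week pattern but gives up the split at Week 100. Relabelling the rows as Week 96 to under Week 108 and Week 108 onward would be consistent, but it would leave an empty last row in an on-treatment table.

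In SAP 4.2.5.1, change Visit 26 to Visit 28 in the second-year completion sentence, to agree with protocol Table 4 and the overall summary.

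The cost is SAP wording and the matching table programs. No data collection, test or sample size changes.
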